### 9.4 Statistical Analyses

The statistical analysis plan (SAP) will be developed and finalized before database lock and will describe the participant populations to be included in the analyses, and procedures for accounting for missing, unused, and spurious data. This section is a summary of the planned statistical analyses of the primary and secondary endpoints.

#### 9.4.1 Efficacy Analyses

For each post-dose time point, Pain Intensity Differences (PID) will be derived by subtracting the pain intensity at the post-dose time point from the baseline intensity score (baseline score – post-baseline score). A positive difference is indicative of improvement. Time-weighted Sum of Pain Intensity Differences (SPIDs) will be calculated for 2, 4, 8, and 12 hours by

multiplying the PID score at each post-dose time point by the duration (in hours) since the preceding time point and then summing these values over 2, 4, 8, and 12 hours, respectively.

Similarly, Total Pain Relief Scores (TOTPARs), will be calculated by multiplying the pain relief score at each post-dose time point by the duration (in hours) since the preceding time point and then summing these values.

In all analyses for participants who take rescue medication, all pain intensity scores after intake of rescue medication will be imputed by the worse of the baseline or the score assessed immediately before taking rescue medication. All pain relief after intake of rescue medication will be imputed by “no relief” (0).

Endpoint	Statistical Analysis Methods
Primary	
The primary efficacy analyses population will be based on the PP population.
 
Sum of Pain Intensity Difference over 8 hours: SPID0-8 be analyzed using an analysis of covariance model (ANCOVA) with treatment as fixed effect and baseline pain intensity score as the covariate. A 95% of confidence interval (CI) for the treatment differences and pairwise p-values will be calculated based on the above mentioned model.

Secondary	
Total Pain Relief over 8 hours: TOTPAR0-8 will be analyzed similarly as for the primary endpoint.
 
Time to first use of rescue medication. If a participant did not take the rescue medication during the treatment period, (s)he will be censored at the time of last assessment. Time to first use of rescue medication will be estimated and plotted using Kaplan-Meier method and analyzed using log-rank test.


Secondary
	
The SPID0-2, 0-4, 0-12 will be analyzed using the same methodology as for SPID0-8.
 
TOTPAR0-2, 0-4, 0-8 and 8-12 will be analyzed using the same methodology as for SPID0-8.
 
Pain Intensity Difference (PID) and Pain Relief scores at 0.5, 1, 1.5, 2, 3, 4, 5, 6, 7, 8, 9, 10, 11, and 12 hours post-dose. Descriptive statistics for each time point and graphical illustrations of the time effect curves will be presented.
 
CCI [REDACTED]
 
The cumulative proportion of participants taking rescue medication over time will be analyzed using Chi-square tests and curves over time will be plotted. Frequency tables will be tabulated for the number of times that the participant took rescue medication over the 12 hour period.
 
Peak PID and peak pain relief will be analyzed descriptively.
 
CCI [REDACTED]
 
Global Assessment of the investigational product will be analyzed using CMH method with modified ridit score.

------------------	---

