### **9.1 Statistical Hypotheses**

The primary efficacy endpoint is the sum of change in pain intensity from 0 to 8 hours (SPID0-8). No multiplicity adjustment will be made. All statistical comparisons will be made at significance level of 0.05.

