### **9.2 Sample Size Determination**

The study is not statistically powered. From operational feasibility point of view, a total of approximately 180 participants (30 participants per active treatment arm and 15 in the caffeine and placebo arms using a 2:2:2:2:1:1 ratio) are chosen, a total of approximately 190 participants will be randomized into the study if a drop-out rate of 5% is assumed.

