6.1.4 Adjustments for Covariates

Baseline pain intensity will be used as a covariate for the efficacy analysis where appropriate.

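### Protocol 9.4.1 names tests without baseline-pain adjustment for time to rescue, cumulative rescue and Global Assessment, and SAP 6.1.4 does not list which endpoints use the covariate; the tests are valid but may lose some power

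*Protocol*

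**What the plan says.** Protocol 9.4.1 analyses SPID0-8 by ANCOVA with baseline pain intensity as covariate, and treats the other SPID and TOTPAR endpoints the same way. Three other secondary endpoints get tests for which no covariate or stratum is named:

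- Time to first rescue: "Time to first use of rescue medication will be estimated and plotted using Kaplan-Meier method and analyzed using log-rank test".
- Cumulative rescue: "The cumulative proportion of participants taking rescue medication over time will be analyzed using Chi-square tests".
- Global Assessment: "Global Assessment of the investigational product will be analyzed using CMH method with modified ridit score".

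The SAP's only visible general rule is in 6.1.4: "Baseline pain intensity will be used as a covariate for the efficacy analysis where appropriate". It lists no endpoints. SAP 6.8.2.2 says that time to rescue will be analysed and shows no method. The method clause in SAP 6.8.2.9 (cumulative rescue) is redacted. The visible text of SAP 6.8.2.11 (Global Assessment) is descriptive only.

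Baseline pain is available for everyone. The Schedule of Activities has the categorical scale and the NRS completed before dosing, and inclusion criterion 9 requires moderate or severe pain and an NRS of at least 5.

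On size and error control, Protocol 9.2 states "The study is not statistically powered" and plans "30 participants per active treatment arm and 15 in the caffeine and placebo arms using a 2:2:2:2:1:1 ratio". Protocol 9.1 adds "All statistical comparisons will be made at significance level of 0.05" and "No multiplicity adjustment will be made".

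**The concern.** Participants who start with worse pain may be expected to ask for rescue sooner and to rate the medication lower. If so, a comparison that ignores baseline pain carries extra variation, and any chance imbalance between small arms stays in it. The ANCOVA deals with this for SPID and TOTPAR; the three tests above, as named, do not.

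Time to rescue is the visible endpoint for the objective on duration of analgesic efficacy. The protocol commits to a 95% CI for the ANCOVA contrasts, but the log-rank test comes with Kaplan-Meier curves and no stated between-arm estimate or interval. In a dose-ranging study without a power calculation, such an estimate would be among the more useful outputs.

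The wording of SAP 6.1.4 also leaves the choice open. Unless the redacted text settles it, someone must later decide for which endpoints the covariate is appropriate, and that is better fixed before unblinding.

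**Working it through.** **1. The plan's own figures.** Five arms of 30 and two of 15 give 5 × 30 + 2 × 15 = 180, and 180 / 0.95 = 189.5, rounded up to 190. Both reproduce. The arm sizes fit the seven-part ratio in Protocol 6.1.1; the ratio printed in 9.2 has six parts for seven arms, a separate point to reconcile. The contrasts of interest are 30 v 30 and 30 v 15.

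**2. Chance imbalance.** Assume that 40% have severe pain (not in the documents) and that allocation is not stratified by pain. The SD of the difference in severe share is sqrt(p(1 − p)(1/n1 + 1/n2)), with p(1 − p) = 0.4 × 0.6 = 0.24.

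- 30 v 30: sqrt(0.24 × (1/30 + 1/30)) = sqrt(0.0160) = 0.126, or 12.6 points.
- 30 v 15: sqrt(0.24 × (1/30 + 1/15)) = sqrt(0.0240) = 0.155, or 15.5 points.

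**3. Log-rank power, unstratified → stratified by moderate/severe.** Simulation with 3,000 to 4,000 trials per setting, two-sided 0.05 (the documents do not state sidedness), exponential times, censoring at 12 h and 40% severe. The treatment hazard ratios and control hazards are assumptions.

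| Rescue hazard, severe v moderate | 30 v 30, HR 0.5, control 0.12/h | 30 v 15, HR 0.4, control 0.25/h |
|---|---|---|
| 1.0 | 56.6 → 55.0% | 76.2 → 74.0% |
| 1.5 | 58 → 58% | 76 → 75% |
| 2.0 | 57 → 60% | 73 → 75% |
| 3.0 | 52 → 63% | 66 → 75% |

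Monte Carlo error is just under 1 point per figure. Repeat runs of these settings gave 0 to −3 points in the first row, about nil at 1.5-fold, +2 to +4 at 2-fold and +9 to +11 at 3-fold.

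**4. A second model, all three endpoints.** Here baseline NRS runs from 5 to 10 (assumed SD 1.47), median control time to rescue is 6 h, treatment HR is 0.5, and the rescue hazard rises by the stated ratio per SD of baseline NRS (4,000 trials each). The adjusted analyses are a Cox model, a logistic model and a rank ANCOVA.

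| Endpoint, contrast | HR per SD 1.0 | 1.2 | 1.5 | 2.0 |
|---|---|---|---|---|
| Time to rescue, 30 v 30 | 55→53 | 55→55 | 51→56 | 42→54 |
| Time to rescue, 15 v 30 | 43→42 | 44→43 | 39→40 | 33→40 |
| Rescue proportion, 30 v 30 | 50→51 | 51→53 | 46→51 | 36→45 |
| Rescue proportion, 15 v 30 | 35→39 | 34→39 | 30→35 | 24→32 |
| Global Assessment, 30 v 30 | 66→65 | 66→66 | 61→64 | 53→61 |
| Global Assessment, 15 v 30 | 48→47 | 48→48 | 46→48 | 39→45 |

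The pattern matches step 3: little change when baseline pain is weakly prognostic, and up to 12 points when it is strongly prognostic. Part of the gain for rescue proportion is not real, because the adjusted logistic test rejected in 5.2 to 6.4% of null trials. A stratified CMH test for that endpoint was not itself simulated.

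**5. Validity of the named tests.** With no treatment effect, the unadjusted tests rejected in 4.1 to 5.5% of trials (log-rank), 4.5 to 5.8% (chi-square) and 4.6 to 5.6% (CMH), whatever the strength of baseline pain.

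**The case against.** The strongest reply is that the visible text cannot show what the final analysis does. Protocol 9 and 9.4 describe 9.4.1 as a summary and defer to the SAP. SAP 6.1.4 provides for baseline pain, and SAP 6.1, 6.1.1, 6.8, 6.8.2.9 and 8 are redacted in whole or part. This stands. A reader might infer that the three endpoints will certainly be tested without adjustment; the documents do not support that. What remains is that the protocol names no stratum and the visible SAP lists no endpoints.

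A reader might also infer that the named tests cannot use baseline pain. That is wrong: the CMH test is a stratified method, and the log-rank test accepts strata. They are simply not named.

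A reader might infer that power is wasted. No document says how baseline pain relates to rescue or to Global Assessment, and eligibility confines it to two adjacent categories and NRS 5 to 10. The larger gains need a strong effect within that narrow range.

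Nor is this an error of validity. Randomization keeps the type I error near 5%, and chance imbalance is already part of the reference distribution. The endpoints are secondary, no visible text ranks time to rescue first among them, and the trial is declared unpowered.

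Two smaller points are fair. Kaplan-Meier estimation does describe each arm, so what is missing is a between-arm estimate with an interval. And Protocol 6 and 6.2 say that dispensing follows the schedule and the pain category. This may describe only the entry requirement, but it is ambiguous; if allocation were stratified by pain, the imbalances in step 2 would shrink and the analysis would have a further reason to use the stratum.

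**Conclusion.** The point holds as one of efficiency and specification. The protocol names an unstratified log-rank test, chi-square tests and a CMH test without named strata, while a baseline measure already collected on everyone is used for SPID and TOTPAR.

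The size depends on an unknown. For the log-rank test, stratifying costs about 0 to 3 points of power if severe pain does not affect rescue, makes about no difference at a 1.5-fold hazard, and gains about 2 to 4 points at 2-fold and about 9 to 11 at 3-fold. This rests on 40% severe pain, exponential times, 12 h of follow-up and the assumed hazards, none of which comes from the documents except the 12 h. The case for a between-arm estimate with an interval does not depend on how prognostic baseline pain is.

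**What to change.** In Protocol 9.4.1 and in SAP 6.1.4, 6.8.2.2 and 6.8.2.9, before unblinding:

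- List in SAP 6.1.4 the endpoints that use baseline pain, and in what form.
- Time to first rescue: stratify the log-rank test by pre-dose categorical pain (moderate or severe) and keep it as the lead test. Add a Cox model with treatment and baseline NRS, labelled supportive, giving the hazard ratio and 95% CI for each contrast. Naming the lead test matters because there is no multiplicity adjustment.
- Cumulative rescue: replace the chi-square test with a CMH test stratified by the same category.
- Global Assessment: name the same stratum for the protocol's CMH test, and reconcile that test with SAP 6.8.2.11, whose visible text is descriptive only.

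If the redacted SAP text already does this, only the protocol wording and the list in 6.1.4 need to be aligned with it.

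The cost is a stratum term and one extra model on existing data. The downside is about 2 to 3 points of log-rank power in the 30 v 15 contrasts if baseline pain turns out not to be prognostic.

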## 9.4.2 Safety Analyses

All safety analyses will be performed on the Safety Population.

Endpoint	Statistical Analysis Methods
Secondary	
AEs produced by severity and relationship to each IMP. Seriousness, severity, relationship to each IMP duration, and outcome will also be listed.
 
Quantitative data for blood pressure, heart rate, body weight, body temperature will be described by summary statistics for the original data as well as for the change from baseline. Frequency tables will be provided for qualitative data. Laboratory data outside the reference range will be listed and highlighted with 'L' for low and 'H' for high. An additional table with all abnormal values will be presented.

## 9.5 Interim Analyses

No interim analysis will be performed.

## 10. Supporting Documentation and Operational Considerations

### 10.1 Appendix 1: Regulatory, Ethical, and Study Oversight Considerations

#### 10.1.1 Regulatory and Ethical Considerations

- This study will be conducted in accordance with the protocol and with the following:
  - Consensus ethical principles derived from international guidelines including the Declaration of Helsinki and Council for International Organizations of Medical Sciences (CIOMS) International Ethical Guidelines
  - Applicable ICH Good Clinical Practice (GCP) Guidelines
  - Applicable laws and regulations

The protocol, protocol amendments, ICF, Investigator Brochure, and other relevant documents (e.g., advertisements) must be submitted to an IRB/IEC by the investigator and reviewed and approved by the IRB/IEC before the study is initiated. Any amendments to the protocol will require IRB/IEC approval before implementation of changes made to the study design, except for changes necessary to eliminate an immediate hazard to study participants.

The investigator will be responsible for the following:

- Providing written summaries of the status of the study to the IRB/IEC annually or more frequently in accordance with the requirements, policies, and procedures established by the IRB/IEC
- Notifying the IRB/IEC of SAEs or other significant safety findings as required by IRB/IEC procedures

- Providing oversight of the conduct of the study at the site and adherence to requirements of 21 CFR, ICH guidelines, the IRB/IEC, European regulation 536/2014 for clinical studies (if applicable), and all other applicable local regulations

### 10.1.2 Financial Disclosure

Investigators and sub-investigators will provide the sponsor with sufficient, accurate financial information as requested to allow the sponsor to submit complete and accurate financial certification or disclosure statements to the appropriate regulatory authorities. Investigators are responsible for providing information on financial interests during the course of the study and for 1 year after completion of the study.

### 10.1.3 Funding

This study will be funded by its sponsor.

### 10.1.4 Informed Consent Process

All relevant information on the study will be summarized in an integrated participant information sheet and informed consent form provided by the sponsor or the study center. Sample participant information and informed consent/assent forms are provided as a document separate to this protocol. Participants 16 to 17 years old who cannot legally give informed consent for research participation must use an IRB-approved assent form and a Parental/Guardian informed consent form. Informed consent must first be obtained from the child's parent or legal guardian before assent may be obtained from the child.

Based on this participant information sheet, the investigator or his/her representative will explain the nature of the study to the participant or his/her legally authorized representative and answer all questions regarding the study. Participants must be informed that their participation is voluntary. Participants will be required to sign a statement of informed consent that meets the requirements of 21 CFR 50, local regulations, ICH guidelines, Health Insurance Portability and Accountability Act (HIPAA) requirements, where applicable, and the IRB/IEC or study center.

The investigator will also mention that written approval of the IRB has been obtained.

Each participant will be informed about the following aspects of premature withdrawal:

- Each participant has the right to withdraw from the study at any time without any disadvantage and without having to provide reasons for this decision;
- The participant's consent covers EOT examinations as specified in the visit description described in Section 7.2 to be conducted after withdrawal of consent;
- The participant's data that have been collected until the time of withdrawal will be retained and statistically analyzed in accordance with the statistical analysis plan;
- Participant-specific data on the basis of material obtained before withdrawal may be generated after withdrawal (e.g., image reading, analysis of biological specimen such as blood, urine or tissues); these data would also be retained and statistically analyzed

in accordance with the statistical analysis plan. The participant has the right to object to the generation and processing of this post-withdrawal data. For this, he/she needs to sign a corresponding declaration of objection; alternatively, the participant's oral objection may be documented in the participant's source data.

Each participant will have ample time and opportunity to ask questions.

Only if the participant agrees to sign the informed consent form and has done so, may he/she enter the study. Additionally, the investigator will personally sign and date the form. The participant will receive a copy of the signed and dated form.

The medical record must include a statement that written informed consent was obtained before the participant was enrolled in the study and the date the written consent was obtained. The authorized person obtaining the informed consent must also sign the ICF. In the event that informed consent is obtained on the date that baseline study procedures are performed, the study record or participant's clinical record must clearly show that informed consent was obtained prior to these procedures.

For minors or adults under legal protection, consent shall be given by the legal guardian(s). The consent of a minor or adult under legal protection shall also be requested where such a person is able to express his/her own will. His/her refusal or the withdrawal of his/her consent may not be disregarded.

The informed consent form and any other written information provided to participants will be revised whenever important new information becomes available that may be relevant to the participant's consent, or there is an amendment to the protocol that necessitates a change to the content of the participant information and / or the written informed consent form. The investigator will inform the participant of changes in a timely manner and will ask the participant to confirm his/her participation in the study by signing the revised informed consent form. Any revised written informed consent form and written information must receive the IRB's approval / favorable opinion in advance of use.

Participants who are rescreened are required to sign a new ICF.

### **10.1.5 Data Protection and Confidentiality**

Any participant records or datasets that are transferred to the sponsor will contain the identifier only; participant names or any information which would make the participant identifiable will not be transferred. The participant must be informed that his/her personal study-related data will be used by the sponsor in accordance with local data protection law. The level of disclosure must also be explained to the participant. The participant must be informed that his/her medical records may be examined by Clinical Quality Assurance auditors or other authorized personnel appointed by the sponsor, by appropriate IRB/IEC members, and by inspectors from national or international regulatory authorities.

All records identifying the participant will be kept confidential and, to the extent permitted by the applicable laws and/or regulations, will not be made publicly available.

Participant names will not be supplied to the sponsor. Only the participant numbers (SNR and RNR) will be recorded in the CRF/eCRF data collection system, and if the participant name appears on any other document (e.g., pathologist report), it must be obliterated before a copy of the document is supplied to the sponsor. Study findings stored on a computer will be

stored in accordance with local data protection laws. As part of the informed consent process, the participants will be informed in writing that representatives of the sponsor, IRB, or regulatory authorities may inspect their medical records to verify the information collected, and that all personal information made available for inspection will be handled in strictest confidence and in accordance with local data protection laws.

If the results of the study are published, the participant's identity will remain confidential. The investigator will maintain a list to enable participants to be identified.

#### **10.1.6 Compensation for Health Damage of Participants / Insurance**

The sponsor maintains clinical trial insurance coverage for this study in accordance with the laws and regulations of the country in which the study is performed.

#### **10.1.7 Committees Structure**

Not applicable

#### **10.1.8 Dissemination of Clinical Study Data**

The sponsor will make the information regarding the study publicly available on the internet at [www.clinicaltrials.gov](http://www.clinicaltrials.gov) as applicable to local regulations.

All data and results and all intellectual property rights in the data and results derived from the study will be the property of the sponsor who may utilize them in various ways, such as for submission to government regulatory authorities or disclosure to other investigators.

Regarding public disclosure of study results, the sponsor will fulfill its obligations according to all applicable laws and regulations. The sponsor is interested in the publication of the results of every study it performs.

#### **10.1.9 Data Handling and Quality Assurance**

The data collection tool for this study will be a validated electronic data capture system to be used at the study site. Participant data necessary for analysis and reporting will be provided to the Sponsor in CDISC (Clinical Data Interchange Standards Consortium) standards.

Clinical data management will be performed in accordance with applicable sponsor's/CRO's standards and data cleaning procedures. This is applicable for data recorded on the CRF/eCRF data collection system as well as for data from other sources (e.g., laboratory).

For data coding (e.g., AEs, medication), internationally recognized and accepted dictionaries will be used.

Reasons for missing data, especially inability to perform a test, must be documented.

All participant data relating to the study, except operative medications will be recorded on a CRF/eCRF data collection system unless transmitted to the sponsor or designee electronically (e.g., laboratory data). The investigator is responsible for verifying that data entries are accurate and correct by physically or electronically signing the CRF.

The investigator must maintain accurate documentation (source data) that supports the information entered in the CRF.

The investigator must permit study-related monitoring, audits, IRB/IEC review, and regulatory agency inspections and provide direct access to source data documents. Monitoring details describing strategy (e.g., risk-based initiatives in operations and quality such as Risk Management and Mitigation Strategies and Analytical Risk-Based Monitoring), methods, responsibilities and requirements, including handling of noncompliance issues and monitoring techniques are provided in the monitoring plan or applicable monitoring SOP.

The sponsor or designee is responsible for the data management of this study including quality checking of the data. The sponsor assumes accountability for actions delegated to other individuals (e.g., Contract Research Organizations).

Study monitors will perform ongoing source data verification to confirm that data entered into the CRF by authorized site personnel are accurate, complete, and verifiable from source documents; that the safety and rights of participants are being protected; and that the study is being conducted in accordance with the currently approved protocol and any other study agreements, ICH GCP, and all applicable regulatory requirements.

Records and documents, including signed ICFs, pertaining to the conduct of this study must be retained by the investigator for 10 years (US), 25 years (Canada) after study completion unless local regulations or institutional policies require a longer retention period. No records may be destroyed during the retention period without the written approval of the sponsor. No records may be transferred to another location or party without written notification to the sponsor.

